#### **8.8.2 Secondary analysis**

- Incidence rate of any SAE.

#### **8.8.3 Exploratory analysis**

- Frequencies and percentages of AEs related to risks defined in the RMP as important potential risks (if available).

#### **8.8.4 Interim analysis**

One interim analysis is planned two years after the last Cerdelga patient has been enrolled in the study.

### **8.9 QUALITY CONTROL**

#### **8.9.1 Data collection, validation and data quality control at MAH/MAH representative level**

Data will be collected using an electronic case record form (e-CRF).

The computerized handling of the data by the MAH/MAH representative may generate additional requests to which the participating Investigator/HCP is obliged to respond by confirming or modifying the data questioned.

Data collection and validation procedures will be detailed in appropriate operational documents.

The purpose of this sub-registry is to collect uniform clinical data on patients with GD on treatment with Cerdelga or Cerezyme.

Data will be collected from enrolled patients by participating HCPs at the time of all patient office visits occurring as per local practice visit schedule or following the recommended schedule of

events of the ICGG Gaucher Registry. A set of CRFs designed for this sub-registry will be used by participating sites. Data collected by sub-registry HCPs or their designees will be submitted to the sub-registry for central processing and evaluation. A primary contact person located at the participating site should be designated as the individual responsible for completing and entering CRFs into the sub-registry database.

### **8.9.2 Data quality control at site level**

Data collected through the sub-registry will be entered into a database and analyzed. Sub-registry staff working with the ICGG Gaucher registry staff will review the data for missing data points, incomplete information, and discrepancies with previously submitted data. If necessary, issues will be resolved with the site by telephone, fax, e-mail, or site visit, as appropriate. Sanofi Genzyme and/or its designee may conduct site visits to review the quality of the sub-registry data, as well as documentation related to institutional review board (IRB)/independent ethics committee (IEC) approvals, informed consent, and any patient authorization documents required by local law.

A clinical monitor from Sanofi Genzyme (or its designee) will manually review data in the CRFs for this safety sub-registry against source documents at the treating HCPs site for validity and completeness. All data captured in the CRFs will be made available to Sanofi Genzyme (or its designee) for data management and analysis. If necessary, the site will be contacted for corrections and/or clarification of the data.

All data management and analysis will occur in a validated computing environment.

Data quality control (site monitoring and/or phone QC) will be performed for 100% of the active sites (which have enrolled at least one patient).

### **8.10 LIMITATIONS OF THE RESEARCH METHODS**

During the clinical studies the frequency of AEs had a tendency to decrease over time. To control for a possible relation between the frequency of AEs and the duration of treatment, AEs will also be analyzed after stratification of patients between three categories of treatment status.

For the sub-registry to meet its goal of providing real-world information on Cerdelga safety, the design of the study must ensure that HCPs report all AEs without preconceived ideas on the safety profile of Cerdelga. To this end no AESI have been specified.

To determine if there are any differences between patients who accept to enroll in the sub-registry and those who do not and, if these differences have any impact on the generalizability of the results, baseline characteristics (including age, sex, genotype, GD history, GD treatment history, current GD treatment and CYPD phenotype) of patients who were enrolled in the safety sub-registry will be compared based on provisions of ICGG Gaucher registry ICF with baseline characteristics of ICGG Gaucher registry patients who did not accept to enroll into safety sub-registry, if this information can be obtained.

Baseline characteristics of subjects who discontinue the study and subjects who complete the study will be summarized in the clinical study report. In addition, number and percent of subjects who discontinue the study will be provided.

The patients enrolled in the ICGG safety sub-registry are not expected to have an extra burden of physician visits or out of the standard of care procedures/tests to comply with, thus any drop out would be mostly expected for reasons not related to the safety sub-registry or for patients who transfer from either Cerdelga and Cerezyme to another GD treatment.

The number of patients for both of the groups who continue their observation in the safety sub-registry will be evaluated annually after the end of the recruitment period to determine the need to replace patients who dropped out of the study for any reason. The need to continue with this requirement will be reassessed two years after the last Cerdelga patient has been enrolled in the study in the interim report.

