### **8.2.3 Analysis population(s)**

Analysis will be performed on the Safety Set, defined as all patients enrolled in the sub-registry who have received at least one dose of Cerdelga or Cerezyme following enrollment.

Category of treatment status at the time of sub-registry enrollment will be defined as:

- a) Patients naive to any GD treatment (ERT or SRT). This category will include, for example, newly diagnosed patients.
- b) Patients naive to the product of interest (Cerdelga in the Cerdelga group and Cerezyme in the comparator group) but experienced to any other treatment for GD (ERT or SRT). This category will include, for example, patients who will switch from any one therapy to the product of interest.
- c) Patients experienced to the treatment of interest. This category will include patients who were on treatment with the product of interest at entry into the sub-registry and then continue this therapy.

Note:

- Patients whose first GD treatment is commercial Cerdelga or Cerezyme, and who enroll in the sub-registry within 3 months of the first dose will be considered treatment naive for the purposes of analysis. Regardless of prior treatment, these patients must receive either Cerdelga or Cerezyme during their participation in the sub-registry.
- Previous exposure to Cerdelga in clinical studies will be considered for any patient of the sub-registry, notwithstanding the group of treatment they belong to during sub-registry participation.
- The data for enrolled patients who switch treatment from Cerdelga to Cerezyme or vice-versa during follow-up will be evaluated to and from the point of switch in the therapy (if applicable).
- A subset of treatment experienced patients will be patients who will switch from any one therapy to any other therapy.
- When available, AEs reported by the patient and in the opinion of investigator related to Cerdelga intake and Cerezyme administration (prior to enrollment into the safety sub-registry) will be collected as part of the patient enrollment characteristics (medical history).

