### **8.3 VARIABLES**

The main analysis of interest will be the incidence rate of any AE report for Cerdelga-treated patients during participation in the sub-registry.

The outcome variable will be a report of an AE, exposure will be duration (in months or years) of time of exposure to Cerdelga while enrolled in the sub-registry, grouping factors will include category of Treatment Status (defined below), duration of GD treatment (including Cerdelga or other GD treatments) prior to enrolling in the sub-registry, selected demographic and baseline characteristics such as age, sex, and genotype as listed in [Section 8.7.5](#).

Category of treatment status at the time of sub-registry enrollment will be defined as:

- a) Patients naive to any GD treatment (ERT or SRT). This category will include, for example, newly diagnosed patients.
- b) Patients naive to the product of interest (Cerdelga in the Cerdelga group and Cerezyme in the comparator group) but experienced to any other treatment for GD (ERT or SRT). This category will include, for example, patients who will switch from any one therapy to the product of interest.
- c) Patients experienced to the treatment of interest. This category will include patients who were on treatment with the product of interest at entry into the sub-registry and then continue this therapy.

Note:

- Patients whose first GD treatment is commercial Cerdelga or Cerezyme, and who enroll in the sub-registry within 3 months of the first dose will be considered treatment naive for the purposes of analysis. Regardless of prior treatment, these patients must receive either Cerdelga or Cerezyme during their participation in the sub-registry.
- Previous exposure to Cerdelga in clinical studies will be considered for any patient of the sub-registry, notwithstanding the group of treatment they belong to during sub-registry participation.
- The data for enrolled patients who switch treatment from the Cerdelga to the Cerezyme or vice-versa during follow-up will be evaluated to and from the point of switch in the therapy.

- A subset of treatment experienced patients will be patients who will switch from any one therapy to any other therapy.
- When available, AEs reported by the patient and in the opinion of investigator related to Cerdelga intake and Cerezyme administration (prior to enrollment into the safety sub-registry) will be collected as part of the patient enrollment characteristics (medical history).

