Data collected in the ICGG Gaucher Registry and sub-registry to be used in this study include:

Upon enrollment into the sub-registry:

- Demographics
  - Gender and date of birth
  - CYP2D6 genotype testing result and date of blood sample collection, if available
- GD history
  - GD diagnosis confirmation
  - Date of diagnosis
  - GD type
- Primary GD treatment history:
  - Date and type of first primary GD treatment
  - Date, dose and type of all past primary GD treatments
  - Start date and dose of Cerdelga or Cerezyme treatment at sub-registry enrollment
- Date of sub-registry enrollment
- Clinically significant medical history (including AEs reported by patient and in opinion of investigator related to Cerdelga intake and Cerezyme administration which occurred prior to enrollment into the safety sub-registry).

At follow-up visits:

No experimental intervention is involved. Participating patients will undergo clinical assessments and receive treatment for GD, as determined by their treating HCPs and using the ICGG Gaucher Registry Recommended Schedule of Assessments as a guideline.

At each follow-up visit the following will be collected:

- Dosing information: including Cerdelga or Cerezyme regimen at the time of follow-up and treatment interruptions for  $\geq 1$  month or regimen changes since last visit with reasons for treatment interruptions or regimen changes.
- Adverse events: information on all AEs ongoing and occurring since the last visit, regardless of seriousness or relationship to Cerdelga or Cerezyme. Adverse events should be collected from patients at least every 6 months. If the period of time between the last ELISAFE sub-registry assessment and the next planned ICGG Gaucher Registry assessment is expected to be more than 6 months, a phone call to inquire about new/ongoing AEs is recommended.

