Analysis of endpoint: The main analysis of interest will be the incidence rate of any AE report for Cerdelga-treated patients during their participation in the sub-registry, considering treatment status at sub-registry enrollment (if applicable). If sufficient data within each treatment status category are collected, incidence rates within treatment status category will be estimated. Similar calculations will be performed for the Cerezyme-treated patients. Summaries will also be presented for three categories of treatment status within each of the Cerdelga and Cerezyme groups (if applicable). The implicit assumption of constant incidence rates over time will be evaluated.

Data will be analyzed as available, missing data will not be imputed. All summaries will be descriptive; no formal hypothesis testing will be performed.

As a part of exploratory analysis, specific analyses of the potential risks in the RMP and any new safety concern that could arise from the sub-registry will be conducted.

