#### Protocol amendment summary of changes table

Section # and Name	Description of Change	Brief Rationale
Throughout	MAH name and address updated.	Administrative update.
PASS information	Name of author and contact details updated.	Administrative update.
Section 4 (Abstract; Rationale and background) and Section 6.2 (Rationale)	Important potential risks: "Vasovagal syncope" and "Off-label use in GD Type 2 and 3" were deleted from important potential risks list. Missing information: "Use in children" was removed from the missing information list.	To align with latest EU RMP V 6.1 (dated 28-Mar-2019).
Section 4 (Abstract, Study design)	Additional text was added to clarify the adult patient population with GD1 as "who have a CYP2D6 Poor Metabolizer (PM), IM, or Extensive Metabolizer (EM) phenotype".	For consistency with body text.
Section 4 (Abstract; Variables)	The following text was added: "The outcome variable will be a report of an AE, exposure will be duration (in months or years) of time of exposure to Cerdelga while enrolled in the sub-registry, grouping factors will include category of Treatment Status (defined below), duration of GD treatment (including Cerdelga or other GD treatments) prior to enrolling in the sub-registry, selected demographic and baseline characteristics such as age, sex, and genotype as listed in Section 8.7.5 ".  Text regarding main analysis of interest was updated to reflect the amendment-specific changes.	Clarification.  Based on the preliminary data surveillance results, analysis by treatment status subgroup may not be possible due to insufficient numbers of patients within subgroups.
	The following text was added: "All summaries will be descriptive. No formal hypothesis testing will be performed."	Clarification
Section 4 (Abstract; Data analysis) and Section 8.8 (Data analysis)	The following text was added under analysis populations: "The analysis will be performed for each treatment group and overall by treatment status (if applicable)."	To complete the description of data analysis.

Section # and Name	Description of Change	Brief Rationale

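### Treatment-status strata fixed at enrollment give only coarse, partial control for time on treatment, and no listed analysis reports the AE rate by time on Cerdelga

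*Combined protocol and SAP*

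**What the plan says.** Section 8.10 states the premise: "During the clinical studies the frequency of AEs had a tendency to decrease over time". It then gives the remedy: "To control for a possible relation between the frequency of AEs and the duration of treatment, AEs will also be analyzed after stratification" by the three treatment-status categories.

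Sections 8.2.3, 8.3 and 8.8 define those categories at a single time point: "Category of treatment status at the time of sub-registry enrollment will be defined as". Category a is naive to all GD treatment. Category b is naive to the product of interest but experienced with another GD treatment. Category c is experienced with the product and is described as "patients who were on treatment with the product of interest at entry into the sub-registry" who then continue it. A note counts as treatment naive "Patients whose first GD treatment is commercial Cerdelga or Cerezyme, and who enroll in the sub-registry within 3 months of the first dose".

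Two other elements bear on duration:
- The abstract (Variables) and Section 8.3 list total duration of GD treatment before enrollment, on any product, as a grouping factor.
- Section 8.8 says: "The implicit assumption of constant incidence rates over time will be evaluated".

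Section 8.8 makes incidence rates within status categories conditional on sufficient data. It splits the data of patients who change product during follow-up at the point of switch. Section 8.7.5 lists among the enrollment data "Start date and dose of Cerdelga or Cerezyme treatment at sub-registry enrollment", and also the dates of all past primary GD treatments.

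**The concern.** The variable that 8.10 wants to control is time on treatment. The variable it uses is a label given at enrollment that contains no measure of time on the product and is never updated. Two consequences follow.

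- A patient who starts at enrollment keeps the same category years later, so each stratum averages the early and late periods that 8.10 says differ.
- The 3-month note applies only when the product is the patient's first GD treatment. Someone who moved from another GD therapy shortly before enrollment is already on the product at entry and joins category c with patients who have taken it for years.

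This bears on the first primary objective, long-term safety, and on long-term use, which Section 6.2 lists as missing information. None of the analyses listed in 8.4 and 8.8 gives the AE rate by time on Cerdelga. The headline result is one overall rate, which rests on a constancy assumption that the protocol's own experience calls into question. A difference between Cerdelga and Cerezyme patients in time on product could also pass into the risk ratio within category c.

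**Working it through.** **Length of follow-up.** Section 5 gives a start in Q2 2018, 32 months of recruitment, and data collection ending four years after the last Cerdelga enrollment. The total is 32 + 48 = 80 months. A May or June 2018 start ends in January or February 2025, which reproduces the plan's Q1 2025; an April start would end in December 2024. Potential follow-up therefore runs from 48 months (4 years, last Cerdelga patient) to 80/12 = 6.67 years. The rationale in the amendment summary gives up to 6.5 years, a difference of no consequence here. Section 8.7.6 sets no minimum participation, so these are potential times and 4 years is not a floor.

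**Applying the category definitions.**

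| Patient at enrollment | Category | Time on product |
|---|---|---|
| Starts the product now, first GD treatment | a | 0 |
| Started 2 months ago, first GD treatment | a (3-month note) | 2 months |
| Switches to the product now | b | 0 |
| Switched to the product 2 weeks ago | c | 2 weeks |
| On the product for 5 years | c | 5 years |

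The last two rows share a stratum, although the fourth patient resembles the third. Prior GD treatment duration does not separate them: ten years of ERT plus two weeks of Cerdelga counts as long.

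**Averaging within a fixed stratum (illustration).** The documents give no rates, so assume a first-year rate R times the later rate, with the later rate set to 1. Over T years from starting, the average is (R + (T − 1))/T = 1 + (R − 1)/T. The share of person-time in the first year is 1/T.

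| T (years) | First-year share | R = 1.5 | R = 2 | R = 3 |
|---|---|---|---|---|
| 2 | 50% | 1.25 | 1.50 | 2.00 |
| 4 | 25% | 1.125 | 1.25 | 1.50 |
| 6.67 | 15% | 1.075 | 1.15 | 1.30 |

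At R = 2, a 100% early excess appears as 50%, 25% or 15%.

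**Mixing within category c (illustration).** Assume a rate of 1 + (R − 1)exp(−t/τ) at t years on product, identical for both drugs. Averaged over follow-up T from starting point t0, this is 1 + (R − 1)(τ/T)[exp(−t0/τ) − exp(−(t0 + T)/τ)]. Take T = (4 + 6.67)/2 = 5.33 years. Put Cerezyme patients at t0 = 10, a share s of Cerdelga patients at t0 = 0.1, and the rest at t0 = 5.

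With R = 2, τ = 1 and s = 50%, the Cerdelga average is (1.169 + 1.001)/2 = 1.085 and the Cerezyme average is 1.000. The apparent ratio is about 1.09 with no true difference; Section 8.6.1 expects a ratio of about 1.2. Over R = 1.5 to 3, τ = 0.5 to 2 years and s = 25% to 100%, the apparent ratio runs from 1.01 to 1.66. Over the same R and τ, in category b, the year-1 rate is 1.2 to 2.2 times the year-5 rate.

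**The case against.** The strongest defence is that the plan does more than stratify. It also groups by prior GD treatment duration and promises to check constancy of rates, and the strata do separate new starters from established users at baseline. Patients who switch at enrollment have their own category b. All of this stands, and it is why the conclusion is partial control and not none. It does not restore what 8.10 claims: the grouping factor is a baseline total across products, and the check has no method, time axis or stated consequence.

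A reader might infer four stronger things that the documents do not support:
- That recent switchers in general are classed with long-term users. This holds only for switches made before enrollment, and the documents do not say how many such patients there are.
- That a patient exposed to Cerdelga in a clinical study has no category on restarting. Section 8.2 says such patients count as experienced, so category c can be read to include them; a clarifying phrase would be enough.
- That enrollment status is carried unchanged past an on-study switch. The data are split at the switch, and the category afterwards is simply not stated.
- That the sponsor expects the strata to be too small. The remark that "analysis by treatment status subgroup may not be possible due to insufficient numbers of patients within subgroups" stands in the change log of amended protocol 03, which Annex 4 says was not implemented. The current 8.8 says only that stratum rates depend on sufficient data.

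It is also fair to say that bands of time on product can be sparse, especially the early ones if few patients are new starters, and that the number of bands is a matter of judgement in a descriptive study.

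**Conclusion.** The concern holds in limited form. Status fixed at enrollment gives coarse, partial control for duration of treatment, and category c mixes pre-enrollment switchers with long-term users. Neither of the other planned elements closes the gap, and the AE rate by time on Cerdelga is not among the listed analyses.

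That conclusion follows from the definitions and needs no assumed rate. Its size cannot be derived from the documents. The figures of 1.5, 1.25 and 1.15 rest on an assumed twofold first-year rate and on patients staying for 2, 4 or 6.67 years; earlier dropout means less dilution. The category c ratios rest on an assumed decay and an assumed mix of patients, and show only that the effect could range from negligible to larger than the expected ratio of 1.2. The point does not invalidate the overall rate, but it should be dealt with before the final analysis.

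**What to change.** 1. In Section 8.8, as the method for the constant-rate check and beside the overall rate, split AEs and person-time by time since first dose of the current product. Let patients enter the risk set at enrollment (delayed entry). Report rates with 95% CIs for each drug in a few pre-specified bands, for example 0-3, >3-12, >12-24, >24-48 and >48 months, with a rule fixed in advance for merging sparse early bands.
2. Use the same axis after an on-study switch. For a patient returning to a product, carry forward the earlier exposure, in line with the plan's intention to take prior Cerdelga exposure into account.
3. Extend the 3-month note in 8.2.3, 8.3 and 8.8 to patients who switched to the product within 3 months before enrollment, so that they count in category b.
4. In 8.10, say that the stratification partly accounts for duration, in place of saying that it controls for it.

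The cost is a little programming and wording, and wide intervals where bands are thin. No new data are needed, because product start dates and past treatment dates are already collected under 8.7.5.
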